## 10.0 Eligibility Screening\*

- 10.1 Describe **screening procedures** for determining subjects’ eligibility.  
Screening refers to determining if prospective participants meet inclusion and exclusion criteria.

 Include all relevant screening documents with your submission (e.g. screening protocol, script, questionnaire).

Response: Screening will occur after the subject signs the consent form by completing the Screening Form. Eligibility can only be confirmed after screening bloodwork results are available.

☐ N/A: There is no screening as part of this protocol.

## 11.0 Recruitment Methods

☐ N/A: This is a records review only, and subjects will not be recruited. NOTE: If you select this option, please make sure that all records review procedures and inclusion/exclusion screening are adequately described in other sections.

### 11.1 Describe when, where, and how potential subjects will be recruited.

*NOTE: Recruitment refers to how you are identifying potential participants and introducing them to the study. Include specific methods you will use (e.g. searching charts for specific ICD code numbers, Research Participant Groups, posted advertisements, etc.).*

Response:

Potential subjects will be recruited by the PI and [name] from their personal clinic patients. Patients will be given a brief verbal overview of the study rationale and procedures. Interested patients will be given a consent form to review at home and contacted within 1 week to answer questions and potentially schedule a screening visit.

### 11.2 Describe how you will protect the privacy interests of prospective subjects during the recruitment process.

*NOTE: Privacy refers to an individual's right to control access to him or herself.*

Response:

The PI will ask potential subjects if and how they wish to be contacted after they have had time to review the consent form. Subjects requesting not to be contacted will not be.

### 11.3 Identify any materials that will be used to recruit subjects.

*NOTE: Examples include scripts for telephone calls, in person announcements / presentations, email invitations.*

 *For advertisements, include the final copy of printed advertisements with your submission. When advertisements are taped for broadcast, attach the final audio/video tape. NOTE: You may submit the wording of the advertisement prior to taping to ensure there will be no IRB-required revisions, provided the IRB also reviews and approves the final version.*

Response:

None.

## 12.0 Procedures Involved\*

12.1 *Provide a description of **all research procedures or activities** being performed and when they are performed once a subject is screened and determined to be eligible. Provide as much detail as possible.*

*NOTE: This should serve as a blueprint for your study and include enough detail so that another investigator could pick up your protocol and replicate the research. For studies that have multiple or complex visits or procedures, consider the addition of a schedule of events table in in your response.*

Response:

PD patients who have had time to review the consent form and have expressed interest in the study will first undergo a screening visit.

**Screening Visit (Visit 1)– performed up to 21 days before Visit 2**

- The study rationale and procedures will be reviewed and all questions answered. The patient's understanding of the study will be confirmed prior to signing of the consent.
- The Screening Form will be completed. If the subject is eligible for the study, the Montreal Cognitive Assessment (MoCA) will be administered.
- About 2 teaspoons (10ml) of venous blood will be obtained from the antecubital or dorsal hand vein for screening blood work (CBC, CMP, TSH, calcium, ESR, urate, HgA1C) performed by Kaleida Laboratory Services. The tests will include a pregnancy test if the subject is female of child-bearing potential.

**Baseline MRI Visit– performed within 21 days after Visit 1**

- This visit will occur at the University at Buffalo's Clinical and Translational Research Center located at [name].
- This brain MRI scan will take about 45-60 minutes of actual scanning to complete.
- There will not be any intravenous injection needed for this scan.
- If the subject is claustrophobic, [name] can prescribe valium to help the subject relax during the scan. If valium is taken, the subject will arrange to have someone else drive them home.

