**Baseline Visit (Visit 2)– performed within 21 days after Visit 1**

- Eligible subjects will receive medium-dose lithium aspartate therapy for 24 weeks with the following dose titration: 10mg bid x 1 week, then 15mg bid x 1 week, then 20mg bid x 2 weeks, then 20mg qAM and 25mg qhs thereafter. Patients will be contacted weekly over the first 4-6 weeks to assess for side effects that are likely to be due to lithium, such as sedation, dizziness or confusion. If side effects occur and are bothersome to the patient, the dose will be decreased incrementally to a minimum of 30mg/day.
- Subjects will receive 24 weeks of study lithium aspartate capsules as well as dosing instructions and study team emergency contact cards. The contact cards will include a list of medications that can interact with lithium that should not be started or changed during the 24-week study. The subject's PMD will be informed of the subject's enrollment if the subject consented to this on the consent form.
- A review of subjects' symptoms and concomitant medications will be recorded.
- The PI will complete the Movement Disorder Society-Unified Parkinson's Disease Rating Scale (MDS-UPDRS) Movement Disorder Society-Unified Parkinson's

Disease Rating Scale (MDS-UPDRS), Part III (Motor Examination) with subjects in the “on” state.

- Subjects will complete the following questionnaires: Parkinson’s Anxiety Scale, Geriatric Depression Scale-15, Fatigue Severity Scale, Insomnia Severity Index and Parkinson’s Disease Questionnaire-8.
- About 8 teaspoons (40ml) of venous blood will be obtained from the antecubital or dorsal hand vein to assess for the following therapeutic targets: PBMC Nurr1 and SOD1 mRNA levels by PCR; PBMC phosphorylated (p) and total (t) levels of pS9 and t-GSK-3 $\beta$ , pThr308, pS473 and t-Akt and plasma interleukin-6 (IL-6) levels. Serum lithium levels will also be assayed the UB Chemistry Instrument Center utilizing an inductively coupled plasma mass spectrometer (ICPMS).

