**Week 24 MRI Visit– performed within 10 days of the Week 24 Visit**

- This visit will occur at the University at Buffalo’s Clinical and Translational Research Center located at [name].
- This brain MRI scan will take about 45-60 minutes of actual scanning to complete.
- There will not be any intravenous injection needed for this scan.
- If the subject is claustrophobic, [name] can prescribe valium to help the subject relax during the scan. If valium is taken, the subject will arrange to have someone else drive them home.

After the Week 24 visit, the study will be completed and subjects will be instructed to stop all study lithium drug. Lithium therapy does not need to be weaned.

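### The scan windows allow a Week-24 MRI up to 10 days after lithium stops and do not place the baseline MRI before the first dose

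*Combined protocol and SAP*

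**What the plan says.** All the timing rules are in Section 12.1 (Procedures Involved).

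- **Baseline scan.** Its heading is "Baseline MRI Visit– performed within 21 days after Visit 1". It is timed from screening only, not from Visit 2 or the first dose.
- **Visit 2.** Its heading is "Baseline Visit (Visit 2)– performed within 21 days after Visit 1", the same window. Lithium is dispensed here: "Subjects will receive 24 weeks of study lithium aspartate capsules". The titration follows: "10mg bid x 1 week, then 15mg bid x 1 week, then 20mg bid x 2 weeks, then 20mg qAM and 25mg qhs thereafter".
- **Final scan.** It is to be "performed within 10 days of the Week 24 Visit", which allows either side of that visit.
- **End of treatment.** "After the Week 24 visit, the study will be completed and subjects will be instructed to stop all study lithium drug".

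Sections 3.0 and 5.1 make the 24-week free-water changes in three brain regions primary MRI outcomes. Section 10.1 holds back confirmation of eligibility until the screening blood results are in. Sections 1.0 and 13.2 give each patient's participation as 25-27 weeks.

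**The concern.** A change from baseline on treatment needs a first scan before drug and a last scan on drug. The plan secures neither.

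The Week-24 end is the clearer problem. The later half of the scan window falls after the point at which patients are told to stop, and the supply covers only the 24 weeks up to that point. No passage carries lithium on until the scan is done. At the baseline end, the scan and the dispensing visit share one window with no stated order, so a scan after the first capsule would still comply.

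Drug status at scanning could matter on the protocol's own account. Section 4.1 links free water to atrophy and inflammation, and reads the pilot's reductions as possibly reflecting less inflammation. Nothing later in the plan would catch a mistimed scan. The only MRI exclusion in Section 5.1 is an occipital free-water change of at least 14%. Neither the ANCOVA in Section 5.1 nor the model in Section 19.1 names scan date, scan interval or drug status. With 15 patients, a few such scans could carry noticeable weight.

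**Working it through.** **Inputs.** Baseline MRI 0 to 21 days after Visit 1. Visit 2 0 to 21 days after Visit 1. Week 24 Visit about 24 × 7 = 168 days after Visit 2. Final MRI from -10 to +10 days around the Week 24 Visit (all Section 12.1). Participation 25-27 weeks (Section 13.2).

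**1. The plan's own figure.** 24 weeks plus 1 to 3 weeks from Visit 1 to Visit 2 gives 25 to 27 weeks. This matches, but it leaves no time for a scan after the Week 24 Visit when the 21 days are fully used.

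**2. Full use of the windows.** 21 + 168 + 10 = 199 days, and 199 / 7 = 28.4 weeks, above the stated 27.

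**3. Does the 27-week limit rule out a late final scan?** 27 × 7 - 168 - 10 = 11 days. A scan 10 days after the visit still fits whenever Visit 2 is within 11 days of Visit 1. So it does not.

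**4. Baseline end, limiting case.** Visit 2 at the start of the window and the scan on day 21 puts the scan 21 days into treatment, or 21 / 168 = 12.5% of it. Dose taken by then on the full titration: 7 × 20 + 7 × 30 + 7 × 40 = 630 mg. Dose over 168 days: 7 × 20 + 7 × 30 + 14 × 40 + 140 × 45 = 7,210 mg. Share: 630 / 7,210 = 8.7%. This is a ceiling, because Visit 2 has to wait for the screening results.

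**5. Both ends mistimed to the limit.** Scan interval 168 - 21 + 10 = 157 days, of which 168 - 21 = 147 on lithium and 10 off.

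**6. Direction and size.** If lithium lowers free water, a baseline scan on drug starts too low and a final scan off drug may have partly rebounded. Both shrink the measured reduction. The size needs an onset and washout course that the documents do not give. As an illustration only, assume that the effect builds linearly over 168 days and that a fraction f of it is lost in 10 days off drug. Apply this to the pilot's medium-dose mean change in the posterior substantia nigra (Table 1: -0.0307, n=2):

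-0.0307 × (147 / 168) × (1 - f)

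| f (assumed) | Measured change |
|---|---|
| 0 | -0.0269 |
| 0.5 | -0.0134 |
| 1 | 0 |

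The range runs from minor dilution to complete loss, so it shows direction and no usable size.

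**7. After the fix.** With the baseline scan before the first capsule and the final scan from day -10 to day 0, the interval runs from 168 - 10 = 158 to 168 + 21 = 189 days. Off-drug days before the final scan are 0. Lithium days before the baseline scan are 0. Longest participation is 21 + 168 = 189 days = 27 weeks, which agrees with Section 13.2.

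**The case against.** The other side has a good case on intent. The first scan is called baseline throughout and is listed ahead of Visit 2. The table in Section 12.2 puts MRI in the Baseline Visit and Week 24 Visit columns. At the final end, the stop instruction sits under the Week 24 MRI heading and says that the study is then complete, so it may have been meant to cover both appointments.

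Most of this stands for the baseline end: a pre-dose scan is very probably intended, and what is missing is the rule. It helps less at the final end. The MRI heading times the scan from the Week 24 Visit, so there the term means the clinic visit as distinct from the scan. Section 14.1 places the scans at a different facility from the clinic visits, so same-day completion cannot be assumed.

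A reader might infer more than the documents support:

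- **That the primary MRI change is contaminated at both ends.** The windows permit mistimed scans and do not require them. The earlier half of the Week-24 window is on drug.
- **That lithium could appear effective because of the timing.** On the investigators' own hypothesis the error runs towards dilution.
- **That a wide scan interval is itself a serious fault.** The extremes are 168 - 21 - 10 = 137 and 168 + 21 + 10 = 199 days. The first needs a final scan before the Week 24 Visit, so it cannot coincide with off-drug days. The second exceeds the stated participation time. At the one-year Parkinson's disease change of 0.0180 in PPMI (Table 1), 31 days amount to 0.0180 × 31 / 365 = 0.0015, against a standard deviation of 0.055.
- **That baseline blood is equally exposed, or that scan dates go unrecorded.** The blood is drawn at Visit 2, the visit at which capsules are handed out, and Section 20.6 already puts date and time on every scan.

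**Conclusion.** The point holds as a gap in the scan windows that should be fixed. It does not show that the MRI outcome is invalid.

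It is firmest at Week 24, where a stated window and a stated stop instruction do not fit together and a compliant scan can be up to 10 days off drug. At baseline the order of scan and first dose is not stated, though the intended order is fairly clear. The worst case of 157 days between scans, 147 on lithium and 10 off, is theoretical. The stated 25-27 weeks and the 28.4 weeks that the windows allow also disagree.

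The expected effect is dilution of the 24-week change. That rests on the assumption that lithium lowers free water and that the effect begins, or fades, within the days concerned. The documents settle neither, so no size can be given.

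**What to change.** Change scan timing only, and leave the dosing and stopping instructions to the investigator.

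1. In Section 12.1, require the baseline MRI to be completed before the first lithium capsule.
2. Set the Week-24 MRI window to on or before the Week 24 Visit, for example day -10 to day 0.
3. Reconcile the headings and text for the baseline MRI, Visit 2 and the Week 24 MRI in Section 12.1 with the participation time in Sections 1.0 and 13.2.
4. In Section 19.1, add a sensitivity analysis of the MRI outcomes that excludes any scan out of order with the first or last dose. The dates and times on scans and blood samples (Section 20.6) already place each scan against Visit 2 and the Week 24 Visit.

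The cost is a short amendment and slightly tighter MRI booking. No extra scan or visit is needed.

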**Baseline Visit (Visit 2)– performed within 21 days after Visit 1**

- Eligible subjects will receive medium-dose lithium aspartate therapy for 24 weeks with the following dose titration: 10mg bid x 1 week, then 15mg bid x 1 week, then 20mg bid x 2 weeks, then 20mg qAM and 25mg qhs thereafter. Patients will be contacted weekly over the first 4-6 weeks to assess for side effects that are likely to be due to lithium, such as sedation, dizziness or confusion. If side effects occur and are bothersome to the patient, the dose will be decreased incrementally to a minimum of 30mg/day.
- Subjects will receive 24 weeks of study lithium aspartate capsules as well as dosing instructions and study team emergency contact cards. The contact cards will include a list of medications that can interact with lithium that should not be started or changed during the 24-week study. The subject's PMD will be informed of the subject's enrollment if the subject consented to this on the consent form.
- A review of subjects' symptoms and concomitant medications will be recorded.
- The PI will complete the Movement Disorder Society-Unified Parkinson's Disease Rating Scale (MDS-UPDRS) Movement Disorder Society-Unified Parkinson's

Disease Rating Scale (MDS-UPDRS), Part III (Motor Examination) with subjects in the “on” state.

- Subjects will complete the following questionnaires: Parkinson’s Anxiety Scale, Geriatric Depression Scale-15, Fatigue Severity Scale, Insomnia Severity Index and Parkinson’s Disease Questionnaire-8.
- About 8 teaspoons (40ml) of venous blood will be obtained from the antecubital or dorsal hand vein to assess for the following therapeutic targets: PBMC Nurr1 and SOD1 mRNA levels by PCR; PBMC phosphorylated (p) and total (t) levels of pS9 and t-GSK-3 $\beta$ , pThr308, pS473 and t-Akt and plasma interleukin-6 (IL-6) levels. Serum lithium levels will also be assayed the UB Chemistry Instrument Center utilizing an inductively coupled plasma mass spectrometer (ICPMS).

**Week 12 phone call- performed about 12 weeks after Visit 2**

- Subjects will be called by a study team member to answer questions, assess for adverse events, assess for changes in concomitant medications, confirm study drug is being taken appropriately and confirm the date and time of the next study site visit.

**Week 24 Visit- performed about 24 weeks after Visit 2**

- Subjects’ adverse events and concomitant medications will be assessed.
- The PI will complete the Movement Disorder Society-Unified Parkinson’s Disease Rating Scale (MDS-UPDRS) Movement Disorder Society-Unified Parkinson’s Disease Rating Scale (MDS-UPDRS), Part III (Motor Examination) in the “on” state.
- The MoCA version 2 will be assessed.
- Subjects will complete the following questionnaires: Parkinson’s Anxiety Scale, Geriatric Depression Scale-15, Fatigue Severity Scale, Insomnia Severity Index and Parkinson’s Disease Questionnaire-8.
- About 2 teaspoons (10ml) of venous blood will be obtained from the antecubital or dorsal hand vein for CBC, CMP, TSH, calcium, ESR, urate, HgA1C and serum lithium performed by Kaleida Laboratory Services.
- About 8 teaspoons (40ml) of venous blood will be obtained from the antecubital or dorsal hand vein to assess for the following therapeutic targets: PBMC Nurr1 and SOD1 mRNA levels by PCR; PBMC phosphorylated (p) and total (t) levels of pS9 and t-GSK-3 $\beta$ , pThr308, pS473 and t-Akt and plasma interleukin-6 (IL-6) levels. Serum lithium levels will also be assayed the UB Chemistry Instrument Center utilizing an inductively coupled plasma mass spectrometer (ICPMS).

**Week 24 MRI Visit– performed within 10 days of the Week 24 Visit**

- This visit will occur at the University at Buffalo’s Clinical and Translational Research Center located at [name].
- This brain MRI scan will take about 45-60 minutes of actual scanning to complete.
- There will not be any intravenous injection needed for this scan.
- If the subject is claustrophobic, [name] can prescribe valium to help the subject relax during the scan. If valium is taken, the subject will arrange to have someone else drive them home.

After the Week 24 visit, the study will be completed and subjects will be instructed to stop all study lithium drug. Lithium therapy does not need to be weaned.

## 12.2 Describe what data will be collected.

*NOTE: For studies with multiple data collection points or long-term follow up, consider the addition of a schedule or table in your response.*

Response:

### Overview of study activities:

	Screening Visit	Baseline Visit	Week 24 Visit
Medical History	X		
MDS-UPDRS		X	X
Questionnaires		X	X
MoCA	X		X
Adverse events and concomitant medications	X	X	X
Blood Test	X	X	X
MRI scan		X	X

MRI scans will be stored using an eXtensible Neuroimaging Archive Toolkit (XNAT) system. XNAT integrates with the MRI scanner via a DICOM Storage Class Provider (SCP) receiver, where the scanner can send DICOMs directly to XNAT. XNAT's DICOM SCP receiver operates on port 8106 behind a firewall allowing only the pre-approved whitelisted IP addresses of the CBI scanners to upload DICOMs. The XNAT system is hosted on a Linux server on Amazon Web Services (AWS), which provides encrypted filesystems in alignment with FedRAMP and NIST 800-53 risk management programs. Users will be given access to XNAT via individual accounts to access the system's web interface over encrypted HTTPS. Access will only be provided to study team members and CBI staff. The web interface is behind a firewall allowing access only from within the UB network. All data transfers, including DICOM transfer initiated by the scanners and web interface access, will be routed through an encrypted VPN tunnel established and administrated by UBIT. The XNAT system will never host any directly identifying information, such as subject names; only subject codes will be used on the scanner to prevent identifying information from being transferred to XNAT. DICOM files will be stored indefinitely on the server's file system, with daily snapshots retained for 14 days.

 12.3 List any instruments or measurement tools used to collect data (e.g. questionnaire, interview guide, validated instrument, data collection form).

*Include copies of these documents with your submission.*

- Response: The screening form, concomitant medication form, subject ID form, subject visit form, UK Blood Bank PD diagnosis form, MDS-UPDRS, Parkinson's Anxiety Scale, Geriatric Depression Scale-15, Fatigue Severity Scale, Insomnia Severity Index and Parkinson's Disease Questionnaire-8 have been included in this submission package.

12.4 Describe any source records that will be used to collect data about subjects (e.g. school records, electronic medical records).

Response: None.

*12.5 Indicate whether or not **individual** subject results, such as results of investigational diagnostic tests, genetic tests, or incidental findings will be shared with subjects or others (e.g., the subject's primary care physician) and if so, describe how these will be shared.*

Response: Individual subject results will be mailed or emailed to subjects after study completion.

*12.6 Indicate whether or not **study** results will be shared with subjects or others, and if so, describe how these will be shared.*

Response: Study results will be shared with subjects by forwarded each a copy of the published manuscript.

### **13.0 Study Timelines\***

*13.1 Describe the anticipated duration needed to enroll all study subjects.*

Response: 7 months.

*13.2 Describe the duration of an individual subject's participation in the study. Include length of study visits, and overall study follow-up time.*

Response: Each subject will participate for 25-27 weeks. Each visit will take 60-90 minutes.

*13.3 Describe the estimated duration for the investigators to complete this study (i.e. all data is collected and all analyses have been completed).*

Response: 12 months.

### **14.0 Setting**

*14.1 Describe all facilities/sites where you will be conducting research procedures. Include a description of the security and privacy of the facilities (e.g. locked facility, limited access, privacy barriers). Facility, department, and type of room are relevant. Do not abbreviate facility names.*

*NOTE: Examples of acceptable response may be: "A classroom setting in the Department of Psychology equipped with a computer with relevant survey administration software," "The angiogram suite at Buffalo General Medical Center, a fully accredited tertiary care institution within New York State with badge access," or, "Community Center meeting hall."*

Response: All subject clinical visits will occur at UBMD Neurology at [name]. This is a clinic where neurology patients are routinely treated. The facility is staffed during business hours and otherwise locked. The MRI visits will occur at the University at Buffalo's Clinical and Translational Research Center located at [name]

14.2 *For research conducted outside of UB and its affiliates, describe:*

- *Site-specific regulations or customs affecting the research*
- *Local scientific and ethical review structure*

*NOTE: This question is referring to UB affiliated research taking place outside UB, i.e. research conducted in the community, school-based research, international research, etc. It is not referring to multi-site research. UB affiliated institutions include Kaleida Health, ECMC, and Roswell Park Cancer Institute.*

Response:

- ☒ N/A: This study is not conducted outside of UB or its affiliates.

